#### Inclusion & Exclusion criteria:

These are the same as in stage 1, except an additional exclusion criteria is: Participated in Stage 1. Criteria for driving will be decided based on results from Stage 1, with COMIRB guidance.

#### Dose escalation strategy:

In each of the two 7-week periods, study product (CBD or placebo) will be started at 5 mg/kg/day and increased as tolerated to a maximum weight-adjusted target dose that is determined as a result of the Stage 1 study. The dose escalation strategy is the same as in Stage 1 for each treatment phase, except that subjects will take 5 mg/kg/day for 10 -15 days, and have a study visit before increasing further. The reason for a range of 10-15 days instead of exactly 10 days is to allow for some flexibility in getting subjects in for the study visit. Then the dose is escalated at 3-day intervals (with 5 mg/kg/day increased each interval) until the subject reaches the maximum target dose or experiences intolerable adverse effects, in which case the dose will be dropped to the last tolerated dose. Tolerability will be assessed on the third day of each dose and the subject is instructed whether or not to change the dose on the next day. The maximal tolerated dose is the dose at which 5 mg/kg/day higher was not tolerated on two trials. When subject achieves the maximal tolerated dose or the maximum targeted dose, they will maintain that dose for 28 +/-4 days.

Urine collection, storage and transfer for cannabis and metabolites test protocol is as described in Stage 1.

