10) population with severe epilepsy. Subjects were evaluated after 12 weeks on study drug, mean dose of ~23 mg/kg/day. Adverse events were reported in 128 (79%) of the 162 patients within the safety group. Adverse events reported in more than 10% of patients were somnolence (25%), decreased appetite (19%), diarrhea (19%), fatigue (13%), and convulsion (11%). Somnolence and fatigue were not dose related, diarrhea and weight loss occurred more often in subjects taking >15 mg/kg/day. Of note, the concomitant use of clobazam (an anticonvulsant medication) was highly associated with somnolence, meaning somnolence was less in those not on clobazam (21%) compared to those taking it (51%). Most adverse events were moderate and transient. SAEs deemed related to the study drug occurred in 12% of subjects, including 9 who had status epilepticus. However, of note, the study showed a ~50% reduction in seizures on study drug, and status epilepticus is a common problem in the population studied. Five subjects (3%) stopped the study drug due to an adverse event. Please see the article regarding clinically significant changes in safety blood analyses. Hepatotoxicity (< 1%), hyperammonemia (<1%), and thrombocytopenia (<1%) occurred only in subjects also taking valproate.

The maximum tolerated doses, in mg/kg/day, of the 10 subjects will be averaged, and adjusted to the next highest 5 mg/kg/day. That dose will be used as the targeted dose for the RCT. For example if the average of the maximal tolerated doses in Stage 1 subjects is 17.4 mg/kg per day, the targeted dose in the RCT will be 20 mg/kg/day. Or if the average of the maximal tolerated doses in stage 1 subjects is 22.7 mg/kg per day, the targeted dose in the RCT will be 25 mg/kg/day.

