### Dose escalation strategy

Study product will be started at 5 mg/kg/day and increased every 3 days by 2.5 mg/kg/day to 10 mg/kg/day. Then increase the dosage every 5 days by 5 mg/kg/day until the subject reaches a maximum targeted dose (20 mg/kg/day) or experiences intolerable adverse effects, in which case the dose will be dropped to the last tolerated dose, for 10-15 days. Tolerability will be assessed on the third day of each dose between 5-10 mg/kg/day and the fifth day of each dose between 10-20 mg/kg/day and the subject is instructed whether or not to change the dose starting the next day. Once a subject has been on a specific dose for at least 3 days (5-10 mg/kg/day) or 5 days (10-20 mg/kg/day), that dose can be changed for less or more than 3 (5-10 mg/kg/day) or 5 days (10-20 mg/kg/day) and can be changed by a smaller increment (2.5-5 mg/kg/day) as needed for tolerability. The maximal tolerated dose is determined by the PI or co-Investigator that is an MD, based on their clinical expertise.

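### The Stage 2 target dose is given as both 20 and 25 mg/kg/day, although Stage 1 stops at 20 and the target rule, rounding up, cannot give more

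*Combined protocol and SAP*

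**What the plan says.** **How the target is set.** Section IV.C.1 gives one rule: "The maximum tolerated doses, in mg/kg/day, of the 10 subjects will be averaged, and adjusted to the next highest 5 mg/kg/day". Two worked examples follow. A mean of 17.4 gives a target of 20. The second supposes "if the average of the maximal tolerated doses in stage 1 subjects is 22.7 mg/kg per day" and gives 25. The Stage 2 dose escalation text in IV.C.3 points back to this rule, since its endpoint is "a maximum weight-adjusted target dose that is determined as a result of the Stage 1 study". The notes to the Stage 2 schedule also say that Stage 1 determines the target.

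**What Stage 1 tests.** The dose escalation strategy in IV.C.2 reads "Study product will be started at 5 mg/kg/day and increased every 3 days by 2.5 mg/kg/day to 10 mg/kg/day", followed by "Then increase the dosage every 5 days by 5 mg/kg/day until the subject reaches a maximum targeted dose (20 mg/kg/day". The tolerability rules that follow confirm the cap: a subject with a grade 1 event who is already on 20 stays on 20.

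**Which Stage 2 dose the rest of the protocol uses.**

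| Place | Dose used |
|---|---|
| IV.C.1, rule for lowering the RCT dose | lowered if the Stage 1 maximum is below 20 |
| IV.C.3, opening paragraph, target | 20 |
| IV.C.3, opening paragraph, dispensing | the 20 mg/kg/day visit supplies the time on 25 |
| IV.E, rule for lowering the RCT dose | lowered if the Stage 1 maximum is below 25 |
| Appendix 1, Stage 2 schedule | 25 on days 22-49 and days 92-119 |

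**Stage 2 steps.** IV.C.3 states "The dose escalation strategy is the same as in Stage 1 for each treatment phase" and names as exceptions only the 10-15 day hold at 5 mg/kg/day and its visit. It then gives "Then the dose is escalated at 3-day intervals (with 5 mg/kg/day increased each interval" and adds "Tolerability will be assessed on the third day of each dose and the subject is instructed whether or not to change the dose". The entry for Visits 4 and 8 puts subjects on 20 mg/kg/day for 5 days.

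**The concern.** Stage 1 exists to find the dose for Stage 2 in people with Parkinson disease, because the protocol says no definitive data exist for adults with a neurodegenerative disease. The Stage 2 schedule and dispensing text nevertheless run to a dose that Stage 1 never gives, and 25 is 25% above its maximum ((25 - 20)/20). IV.C.1 itself cites animal support to 24 mg/kg/day and human literature to about 21.

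Safety and tolerability is the Stage 2 primary outcome, and adverse events are compared at each dose level. Site staff and the data safety monitoring board therefore need one answer on the top dose, on when it is lowered, and on what is dispensed. The text gives two answers to the first two questions, and a supply instruction that fits only 25.

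**Working it through.** **1. Reproduce the plan's examples.** With target = 5 × ceil(mean/5), 17.4 gives 5 × 4 = 20 and 22.7 gives 5 × 5 = 25. Ordinary rounding up reproduces both examples.

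**2. Bound on the mean.** Each of the 10 maximum tolerated doses is at most 20, so the mean is at most (10 × 20)/10 = 20.0. A mean of 22.7 is impossible, and rounding up gives at most 5 × ceil(20/5) = 20.

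**3. The tie.** If *next highest* means strictly higher, a mean of exactly 20.0 gives 25. That mean needs all 10 subjects at 20. A single subject at 17.5 gives (9 × 20 + 17.5)/10 = 19.75, hence 20 under either reading. So 25 has one route, and the examples do not settle it because neither falls on a multiple of 5.

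**4. The thresholds.** A Stage 1 maximum below 20 (IV.C.1) may or may not occur. A maximum below 25 (IV.E) always occurs under a cap of 20, so that condition decides nothing.

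**5. Nominal steps in the two stages.**

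| Dose (mg/kg/day) | Stage 1 days | Stage 2 days per the IV.C.3 steps |
|---|---|---|
| 5 | 1-3 | 1-10 |
| 7.5 | 4-6 | not used |
| 10 | 7-11 | 11-13 |
| 15 | 12-16 | 14-16 |
| 20 | from 17 | from 17 |

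The hold at 5 is not the only difference: 7.5 is skipped, and 10 and 15 last 3 days instead of 5. The dose of 20 is reached on day 17 in both stages.

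**6. Phase ends.** Inputs: 10 days at 5, 3 days per step, 28 days at target, 21 days of washout. The second end is first end + 21 + first end.

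| Target | First end | Second end |
|---|---|---|
| 15 | 10+3+28 = 41 | 41+21+41 = 103 |
| 20 | 10+3+3+28 = 44 | 44+21+44 = 109 |
| 25, 3 days at 20 | 10+3+3+3+28 = 47 | 47+21+47 = 115 |
| 25, 5 days at 20 | 10+3+3+5+28 = 49 | 49+21+49 = 119 |

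The Visit 5 and Visit 9 entry states 47 and 115, and the schedule's day row states 49 and 119. Both sets fit a target of 25. They differ from each other only in the days at 20.

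**The case against.** **The figures are provisional.** IV.C.3 and the schedule notes defer to the Stage 1 result, and the notes call the day and week rows variable. This stands in part: on a round-up reading the governing rule prevails and nobody takes 25. A reader might infer that about 50 subjects will be dosed at 25, and the documents do not support that. But a provisional schedule should show a dose that its rule can normally produce, and deferring to Stage 1 does not reconcile two thresholds or settle the tie.

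**Stage 2 escalation can be followed as written.** This stands. IV.C.3 gives complete steps with a day-3 check and a step back. Stage 1 is also flexible: after a grade 1 event the dose may rise by up to 5, and timing and increments may vary once the minimum days are served. A reader might infer that the 3-day steps add risk. The documents do not show it: 20 is reached no sooner than in Stage 1, and Stage 2 has its own tolerability checks. The fault is an inaccurate label.

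**The days at 20 hardly matter.** Largely right. The conflict arises only with a target of 25, and 2 days lie inside the ±4 day window. A reader might infer that resupply for 25 could come after the move to 25. That combines the general 3-day step with a visit allowed on days 2-5. Under the 5-day rule given for that visit, every permitted day precedes the move.

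**There is experience at and above 25.** Also true. Section III reports single doses in healthy volunteers stated as 21 to 85 mg/kg, Table 2 covers daily doses up to 25, and IV.C.1 cites an epilepsy cohort with a mean near 23. None of these is repeated dosing in Parkinson disease. They could support a deliberate choice of 25, but the protocol does not make that case.

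**Conclusion.** Wrong as written. The rule in IV.C.1 and the Stage 1 cap allow a mean of at most 20.0 and, on rounding up, a target of at most 20. The 22.7 example, the dispensing for 25, the threshold of 25 and the 28 days at 25 per phase do not fit them. These are dosing, dispensing and dose-reduction instructions, so the conflict should be resolved before Stage 2.

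The conclusion rests on the stated Stage 1 cap of 20 and on the examples' rounding. The exception is a strictly-higher reading with all 10 subjects at 20. How likely that is depends on a tolerance rate that the documents do not give, and the point does not need it: the tie rule is missing either way. The *same as Stage 1* label and the days at 20 are minor. The point claims no added harm from the 3-day steps.

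**What to change.** 1. In IV.C.1, define the target as the mean Stage 1 maximum tolerated dose rounded up to a multiple of 5, with a mean of exactly 20 giving 20, so that it never exceeds the highest dose tested in Stage 1. Replace the 22.7 example.
2. Make the reduction rule in IV.C.1, the opening of IV.C.3, IV.E and the Stage 2 schedule refer to the target per IV.C.1 in place of a fixed 20 or 25. Remove the 25 columns.
3. Restate the phase ends as days 44 and 109 for a target of 20 (41 and 103 for 15). Check the Visit 4/8 and 5/9 entries, the schedule notes and the week labels in IV.A. With a target of 20, phase 2 starts on day 44 + 21 + 1 = 66, so its low dose visit on day 75 falls in week 11 and its end on day 109 in week 16, not weeks 12 and 17.
4. Tie the mid-phase supply visit to reaching the target or maximum tolerated dose, not to 20, so that resupply still works at a lower dose. Change the IV.C.3 fallback for subjects who do not reach 20 from 10-15 days to the 28 ± 4 days that the escalation text requires.
5. In the Stage 2 escalation text, replace the statement that it matches Stage 1 with the actual steps: 5 for 10-15 days, then +5 every 3 days.
6. If the sponsor does intend 25, say that Stage 1 does not test it, justify it, and set one number of days at 20 with the visit before the move: 5 days (ends 49 and 119), or 3 days with the visit on day 2 or 3 (ends 47 and 115).

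The cost is a text amendment, with no extra patients or visits. At a target of 20 each phase is 3 to 5 days shorter than now stated (44 against 47 or 49). A 15-day hold makes it 49, so about 7 weeks still holds. The price is that 25 mg/kg/day is given up unless the sponsor explicitly justifies it.

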#### Procedures at each visit

Visit 1- Screening visit: Consent, demographics, concomitant medications, formal drug interaction assessment, family medical history, medical history & physical examination (complete physical exam and

detailed neurological exam), vital signs, orthostatic blood pressures, tremor evaluation, MDS-UPDRS III, H&Y rating, MOCA, Drug, alcohol and tobacco abuse screening test, safety assessments (as listed in section IV A, except for RBDSQ, IRLS, PDQ-39 and EQ-5D), EKG and safety labs (as in dose escalation study), blood cannabis analysis testing, serum pregnancy test (for women childbearing potential) and inclusion/exclusion criteria are done. Study subjects are instructed not to take cannabis from outside source throughout the study.

Visit 2- Baseline visit: Eligibility confirmation (including tremor evaluation), medical history, concomitant medications collection, formal drug interaction assessment, vital signs, orthostatic blood pressures, brief physical exam, MoCA, MDS-UPDRS, H&Y rating, UDysRS, RPW, cognitive assessment battery (including tests of verbal intellectual function, attention, processing speed, executive function, verbal learning and memory, visuospatial memory, speeded verbal fluency and word retrieval), RBDSQ, C-SSRS, IRLS, PDQ-39, EQ-5D, urine drug (THC) test (urine dipstick test), urine pregnancy test (women childbearing potential) and study drug dispensing is done and, if appropriate, randomization. Home diary is also dispensed. Subjects take the first dose and are instructed on how to take the medication and how to fill out the diary at home. Subjects will be monitored and vital signs and orthostatic blood pressures will be checked at 1 hour after taking the study drug. Subjects are also told to bring in empty, partially used and unused bottles of study drug at next clinical visit. Subjects will be told not to take the study drug on the day of the next visit, as they will take it upon arrival under instruction by study staff. Subjects will be given two urine cups, 100 mL each, and will be instructed to collect their urine the morning of the low dose visit. They are asked to fill each cup at least 3/4 full, if possible and to bring them to the visit (no refrigeration needed).

Visit 3 and Visit 7-Low dose visit (end of 10 days on 5 mg/kg/day): On the morning of the visit, subjects will collect their urine and bring it to the visit. Study coordinator will collect and store the urine cups in a -80°C freezer until shipment. Concomitant medications, formal drug interaction assessment, change in medical history, vital signs, orthostatic blood pressures, brief physical exam, MDS-UPDRS, UDysRS, H&Y rating, RPW, Anxiety short form, Depression short form, Emotional and behavioral dyscontrol short form, Fatigue Severity Scale, Pain Intensity and Interference short form, MoCA, RBDSQ, QUIP-RS, C-SSRS, NPI, SCOPA-sleep, IRLS, EQ-5D, PDQ-39, CGI, PGI, and urine pregnancy test are done. Study drug compliance check, adverse event check and blinding assessment are done. Subjects will take their study drug upon their arrival to the clinic and record the taking time. Blood is drawn for cannabis testing and safety labs 3 hours after the dose. Subjects will be monitored and vital signs and orthostatic blood pressures will be checked at 1 and 3 hours after taking the study drug. Home diary is collected and reviewed. The next study drug supply and home diary are dispensed. Subjects are instructed on how to fill out the diary at home and are told to bring in empty, partially used and unused bottles of study drug at next clinical visit. Subjects will again be given urine cups and instructions.

Visit 4 and Visit 8-20 mg/kg/day Assessment visit: Subjects will be on 20 mg/kg/day for 5 days. They will come back to clinic on either day from 2nd through 5th day while on 20 mg/kg/day. On the morning of the visit, subjects will collect their urine and bring it to the visit. Study coordinator will collect and store the urine cups in a -80°C freezer until shipment. Medical history and concomitant medications collection, formal drug interaction assessment, vital signs, orthostatic blood pressures, brief physical exam, CGI, PGI, and adverse event (including SCOPA-Sleep and C-SSRS) check are done. Blood is drawn for complete metabolic profile. Study drug is collected and counted. Study drug is dispensed: and subject is instructed in how to take it. Home diary is collected and reviewed. The next home diary is dispensed. Subjects will be told not to take the study drug on the day of the next visit, as they will take it upon arrival under instruction by study staff. Subjects will again be given urine cups and instructions.

Visit 5-End of first 7-week (47 days) and Visit 9-second 7-week (115 days) treatment phase assessment visits: Same procedures are conducted as at the previous low dose visit, except for study drug and home diary dispensation. In addition, complete physical exam, detailed neurological exam, blood draw, urinalysis, ECG, and full cognitive assessment battery are done. Subjects will take their study drug upon their arrival to the

clinic and record the taking time. Blood is drawn for cannabis testing and safety labs 3 hours after the dose. Subjects will be monitored and vital signs and orthostatic blood pressures will be checked at 1 and 3 hours after taking the study drug.

Visit 6-Start of second 7-week treatment phase: Study drug and home diary dispensation and instruction will be performed. Formal drug interaction assessment will be done. Subjects take the first dose of study drug. Subjects will be monitored and vital signs and orthostatic blood pressure will be taken at 1 hour after taking the study drug. Subjects are also told to take study drug and record the taking time upon their arrival to clinic on the next clinical visit day.

Visit 10-Safety follow up: Vital signs, orthostatic blood pressures, history & complete physical examination, concomitant medications collection, formal drug interaction assessment, MDS-UPDRS, H&Y rating, UDysRS, RPW, MoCA, RBDSQ, QUIP-RS, C-SSRS, NPI, SCOPA-sleep, Anxiety short form, Depression short form, Emotional and behavioral dyscontrol short form, Fatigue Severity Scale, Pain Intensity and Interference short form, IRLS, PDQ-39, EQ-5D-5L, adverse event check, urine pregnancy test and cannabis lab testing are done. Hematology, complete metabolic profile, urinalysis and EKG will be done if there was a clinically significant change at the high dose evaluation visit compared to baseline visit. The PI will evaluate the subject for signs of withdrawal.

#### **C.4 Study Drug: Epidiolex:**

Purified CBD from GW is a strawberry flavored liquid, in sesame oil, provided as 100 mg/ml, extracted from high CBD plant material. The placebo is the same, but without CBD. The study drug is best taken fasted, as food will increase Cmax and delay Tmax. The study drug could be taken with a small amount of food as needed if the subjects experience nausea. It is to be taken twice daily at a standard time, minimum of 6 hours apart. Subjects are instructed to take it before breakfast (30 to 60 minutes) and the same before dinner. Further detail is proprietary. Subjects are instructed not to drink grapefruit for 7 days prior to the first dose of study medication and during the rest of the study (both Stages).

The study drug is taken as normal on the mornings of assessments. As far as practical, the same assessor carries out assessments at each visit. Assessment data are stored and not made available at subsequent visits.

Subjects take their routine anti-PD medication on the day of clinical visit, and when ON (PD medications are working) the testing is done.

CBD and metabolite levels will be measurements:

- In Stage 1, blood CBD and metabolite levels will be measured at the screening visit, final assessment visit and safety follow up visit. Urinary CBD and metabolites levels will be tested at the final assessment visit.
- In Stage 2, blood CBD and metabolite levels will be measured at screening visit, baseline, low dose visit (end of 10 days on 5 mg/kg/day) and end of each treatment phase assessment visits. Urinary CBD and metabolites levels will be tested at the low dose visit, 20 mg/kg/day visit and the end of each treatment phase assessment visit.

## Potential drug-drug interactions

The PI has worked with [name], Pharm D, and GW to study possible drug interactions. See GW Pharmaceutical's Investigator Brochure on CBD, especially pages 4-5, 47-51 and 105-106 and their CBD;CBD BDS Development Core Safety Information dated August 2015 pages 2-4 for detailed information. Also, Appendix 2 is a list of drugs with potentially interactions with CBD, thus the PI will monitor for clinical effects. CBD concentrations and adverse events will be monitored in the presence of concomitant medications which are inhibitors of CYP3A4 and 2C19.

There are many possible interactions, but some are more likely and clinically relevant. Thus, the PI will especially monitor for clinical symptoms that may be associated with these particular interactions. The following drugs may increase the level of CBD: fluoxetine, fluvoxamine, fluconazole, ticlopidine and nefazodone. The following drugs may decrease the level of CBD: carbamazepine, phenytoin, phenobarbital, rifampin and St. John's Wort. The following drugs may interact with CBD to cause their levels to increase: alprazolam, clonazepam, lorazepam, oxazepam, temazepam, zolpidem, clopidogrel, narcotics (codeine, methadone, oxycodone, hydromorphone, morphine), cyclosporine A, tacrolimus, propranolol and acetaminophen. Subjects will be instructed not to take more than 1 gram per day of acetaminophen.

CBD is a potent inhibitor of CYP2C19. The plasma level of clobazam, which is metabolized by CYP2C19, therefore is expected to increase if CBD is added. Clobazam, per Micromedex, causes somnolence (16-25%). In a recent study, *Lancet Neurology* 2016;15:270-278, using the same study drug as in our trial at similar doses there was ~twice as much somnolence AEs reported in subjects on both CBD and clobazam than in subjects on CBD and not clobazam. Thus clobazam will be exclusionary in this study.

The following is additional information relevant to the population of this study, Parkinson disease (PD).

CBD is metabolized by the hepatic CYP450 enzymes 2C19 and 3A4 and an inhibitor of these isoenzymes. Thus the expectation is that selegiline levels could increase. CBD may mildly induce the expression of 1A2, 2B6, and 3A4. Thus the expectation is that levels of rasagiline, ropinirole and selegiline may decrease.

CBD is a relatively potent inhibitor of UGT1A9 and UGT2B7 and has no significant effect on other UGT isoenzymes. The expectation is that the level of rotigotine may increase.

CBD is highly protein bound, so rasagiline, selegiline and rotigotine levels may increase transiently.

Checking plasma concentration levels of these anti-PD medications is not a routine clinical practice. Thus the PI will monitor subjects on these medications for clinical changes. The most important and likely adverse effects of a clinically significant increase in the level of selegiline is anxiety, dyskinesia, agitation, insomnia and hallucinations. The most important and likely adverse effects of a clinically significant decrease in the levels of rasagiline, ropinirole and selegiline is an increase in the motor symptoms of Parkinson disease, which are resting tremor, bradykinesia, rigidity and postural instability. The most important and likely adverse effects of a clinically significant increase in rotigotine is low blood pressure, somnolence and impulse control disorders.

